Sleep to prevent evolving affecting disorders (SPREAD)

NCT02988375

Approved on March 8th 2016

1. PURPOSE: State in one or two sentences the purpose or objective of this project. The purpose of this study is to determine the effectiveness of Digital Cognitive Behavior Therapy for Insomnia (dCBTI) in preventing the incidence of depression among individuals with insomnia.
2. SPECIFIC AIMS: Number your aims so that the aims can be referred to in the Project Design and Data Analysis sections of this outline. Specific aim 1: to assess the efficacy of dCBTI for the prevention of incident depression among individuals with insomnia. Specific aim 2: to determine the moderating effects of health/SES disparities on the efficacy of the dCBTI intervention.
3. RATIONALE FOR THE PROJECT: a. State the rationale for the project and support it with background information about the project. Critically evaluate existing knowledge, and specifically identify the gaps in knowledge the project will fill. A growing body of research indicates that treatment for insomnia may also help prevent the onset of depression (Falussy, Balla & Frecska, 2014). However, CBTI, the current first-line treatment for insomnia, is under-utilized due to a shortage of providers, time- and cost-constraints, and the stigma associated with mental-health treatment (Fields, Schutte-Rodin, Perlis & Meyer, 2013). Digital, internet-delivered forms of CBTI (dCBTI) can overcome these obstacles to make access more widespread, reduce health-care costs, and serve as a sustainable population-level prophylactic treatment for depression. b. State the applicant's prior research and experience in this research area. [name] has a broad background in clinical psychology, with specific training and expertise in sleep medicine. He is an Associate Editor for the journal SLEEP and has authored over 100 peer-reviewed original articles, reviews, and chapters, focused on sleep. He recently served as Chairman of the National Sleep Foundation. [name] has been funded by the NIH to study vulnerability to insomnia and triggers of insomnia (i.e. life stressors). [name] is board certified in CBT-I Treatment to successfully treat insomnia with the long-term goal of preventing incident depression. His experience in this area will make it possible to recruit and retain participants for this research study focusing on insomniacs and depression prevention efforts.
4. SIGNIFICANCE: State concisely the importance of this project by relating the purpose to broader, long-range objectives. Depression is among the most prevalent mental health disorders and carries the heaviest burden of disability among the mentally ill, accounting for roughly 8% of all U.S. years lived with disability (Murray, Atkinson, Bhalla, et al., 2010). Thus, prevention efforts are a major public health concern. According to a recent meta-analysis of over 20-longitudinal studies, the risk of depressive onset among individuals with insomnia is nearly three times that for healthy sleepers (Baglioni, Battagliese, Feige, et al., 2011). Specifically, CBTI is recognized as an effective treatment for insomnia and has also been shown to improve comorbid depression (Manber, Bernert, Suh, Seibern & Ong, 2011; Wu, Appleman, Salazar & Ong, 2015). Combined, these results indicate that the early treatment for Insomnia via CBTI has strong potential for the prevention of depression (Falussy, Balla & Frecska, 2014). However, there are a number of barriers that hinder widespread access to CBTI. Two main problems include access to CBTI health care providers as well as the availability of enough health care providers to meet

he population demands for face-to-face therapy sessions. Thus, digital CBTI (dCBTI), which relies on web and mobile technology, can overcome these obstacles to widespread delivery, reduce patient load on current providers, and reduce health-care costs. Through dissemination of dCBTI, health care will have the potential to treat mental illness post-onset. Overall, this study will serve to determine the effectiveness of using an online CBT-I Treatment to successfully treat insomnia with the long-term goal of preventing incident depression.

5. SUBJECTS IN THE PROJECT: a. State the inclusion and exclusion criteria for enrollment of subjects. Inclusion factors for the patient group will be subjects who have Insomnia and have opted for behavioral treatment for insomnia as therapy at recruitment. Exclusion criteria for subject group includes the presence of unstable chronic medical conditions or mental health conditions that would interfere with the study protocol as well as the presence of moderate depression (QIDS > 15) at recruitment. The history of sleep disorders other than insomnia by self-report will be assessed and used as covariates in analyses; subjects presenting with a history consistent with obstructive sleep apnea (OSA) or restless leg syndrome (RLS) or other sleep disorders will be identified based on standardized questionnaires. b. Describe the control population (if utilized) and justify its selection. The control for this study will be an "information control" treatment group. Subjects will be emailed sleep tips and sleep-related information. c. Support the likelihood of recruiting the number of subjects required to complete the project. Relate this to other projects recruiting similar subjects. Participants will be recruited from several well-developed sources, including the HFHS Sleep Center Clinical database. We maintain a large and representative database (N=7608) of prior participants who have volunteered to be contacted for clinical trials. Preliminary analyses suggest that a large proportion of this database (N=2590) meets primary inclusion criteria for this proposal (current insomnia but no depression). These individuals will be contacted by phone and/or email for potential participation pending a screening assessment. We believe that based on the success we have seen in previous studies (IRB#5544 and #8447), we will be able to complete this protocol within two years following IRB approval.

6. PROJECT DESIGN AND PROTOCOL: a. Describe the experimental design/methodology. This is a randomized parallel group study with group 1 getting CBT-I treatment for insomnia by an online program (Sleepio) and group 2 getting information control sleep tips. Insomnia and other sleep-related symptoms will be assessed at pre treatment, post treatment and at 1-year follow-up. Sleepio can be accessed at www.sleepio.com. Click "Log In" at top right corner and enter email "[contact]" and password "password". b. Outline the protocol, corresponding it to the specific aims; identify the data or endpoints to be analyzed to reach the specific aims. Our primary aim is to maximize and/or improve sleep efficiency in patients (number of hours asleep over number of hours in bed) and to shorten sleep latency (amount of time taken to fall asleep). The primary aim will be to reduce the incidence of depression. Other secondary measures will be taken regarding aspects other than sleep in patients. These will be recorded through the surveys mentioned above and will measure symptom improvements in severity of depression and work productivity. c. Discuss potential limitations and difficulties in the protocol. We do not anticipate any limitations to the current protocol. d. Provide a tentative schedule for conducting and completing this project and, if applicable, the multicenter study. We plan on starting data collection between February 25 and March 1, pending IRB approval. e. Data collection: Submit a copy of the data collection tool or list the data fields to be collected (review IRB policy, Access to Medical Records for Research).Attached in appendix.

7. DATA ANALYSIS: Describe the analysis of the data and relate this to the specific aims in detail. Case reports and medical record reviews also require a description of the planned data analysis (ie. descriptive, observational). The Committee recommends free consultation with the Division of Biostatistics and Research Epidemiology before IRB submission. The following data analysis plan was developed in conjunction with [name], biostatistics section. A logistic regression will be used to assess the association between treatment group and depression status at 1 year. This approach allows inclusion of covariates in the model. We plan on enrolling a total of 300 subjects per group. This results in the analysis having 85% power, with a two-sided alpha level of 0.05, to detect an odds ratio of 2.7 corresponding to rates of depression at 1 year of 10% and 4%. Stratified analysis assuming an equal split of the population, will have 85% power to detect an odds ratio of 10.0. This corresponds to a difference in rates from 10% to 1% which is what we anticipate.

8. JUSTIFICATION FOR NUMBER OF SUBJECTS OR DATA: a. State the number of subjects or data points to be analyzed in the project at this institution and the total number for multicenter studies. The Committee recommends consultation with the Division of Biostatistics and Research Epidemiology [contact]. The proposed sample size of 300 per group (n=600) will yield > 85% power to detect effects with a two-tailed 0.05 alpha level. b. Describe the statistical justification for this number of subjects or data points. The primary hypothesis i.e., risk of depression incidence in the dCBT group relative to the control group will be analyzed using a multivariate logistic regression model. Group differences in continuous outcomes (e.g., SOL, TST, WASO; see STRATEGY section for a full list of quantitative measures) will be tested using ANCOVA models. Power. We anticipate a 14.6% rate of incident depression in the control group, compared to 6.7% in the treatment group.²¹ The proposed sample size of 300 per group (n=600) will yield > 85% power to detect effects with a two-tailed 0.05 alpha level.

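### The entry criterion asks for people who have chosen behavioral insomnia treatment, and nothing listed bars a current or scheduled course of CBT-I, so uptake among controls could dilute the comparison

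*Combined protocol and SAP*

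**What the plan says.** Section 5a sets two conditions for entry: insomnia, and that subjects "have opted for behavioral treatment for insomnia as therapy at recruitment". For exclusions it says: "Exclusion criteria for subject group includes the presence of unstable chronic medical conditions or mental health conditions that would interfere with the study protocol", and adds "the presence of moderate depression (QIDS > 15) at recruitment". A history of sleep disorders other than insomnia is collected for use as a covariate. Section 5a says nothing about past, current or planned treatment of the insomnia itself.

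The control condition in section 5b is information only: "Subjects will be emailed sleep tips and sleep-related information". Section 6a describes a randomised parallel-group design with assessments before treatment, after treatment and at 1 year. Section 7 compares depression status at 1 year by logistic regression, with 300 subjects per group.

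On recruitment, section 5c says: "Participants will be recruited from several well-developed sources, including the HFHS Sleep Center Clinical database".

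Sections 7 and 8 make no allowance for treatment obtained outside the trial, and section 6c anticipates no limitations.

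**The concern.** The criterion selects for wanting the active ingredient. Taken at face value, it lets in a person who is attending CBT-I or has a course arranged. If that person is randomised to the sleep tips, nothing in the text supplied prevents the outside course from going ahead during the follow-up year. The dCBTI arm already receives this type of therapy, so outside uptake would matter mainly among controls. It would bring the control rate of depression closer to the dCBTI rate.

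The as-randomised comparison would then still be valid as a comparison of assignments. It would, however, understate the effect of dCBTI against information alone, and the sample size has little or no reserve for that. If outside treatment were also not recorded, a null result would be harder to interpret, because the amount of treatment among controls would be unknown.

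**Working it through.** **Inputs.** Section 8 anticipates 14.6% depression in controls and 6.7% in the treatment group. Section 7 uses 10% and 4%. Both use 300 per group and a two-sided alpha of 0.05. The crossover share c is not in the documents and is assumed here over a range of 0 to 30%.

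**Formula.** Let p_c be the control rate, p_t the treatment rate, d = p_c − p_t and p̄ = (p_c + p_t)/2. Then SE0 = √[2p̄(1 − p̄)/300], SE1 = √{[p_c(1 − p_c) + p_t(1 − p_t)]/300}, and power = Φ[(d − 1.96·SE0)/SE1]. This is unadjusted, with no covariates.

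**The plan's own figures first.**
- Section 8: d = 0.079, p̄ = 0.1065, SE0 = 0.02519, SE1 = 0.02498. Then (0.079 − 1.96 × 0.02519)/0.02498 = 1.186, giving 88.2%. This agrees with the stated figure of more than 85%.
- Section 7: d = 0.06, p̄ = 0.07, SE0 = 0.02083, SE1 = 0.02069. Then (0.06 − 1.96 × 0.02083)/0.02069 = 0.927, giving 82.3%. The stated figure is 85%. The arcsine formula gives 83.9% and the likelihood-ratio test 83.3%, both close enough to count as reproduced.

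**Dilution.** Suppose a share c of controls obtains CBT-I elsewhere and takes on the dCBTI rate. The control rate becomes p_c − c(p_c − p_t). For section 8 at c = 10%: 14.6 − 0.10 × 7.9 = 13.81%, so the difference falls from 7.9 to 7.11 points. For section 7 at c = 10%: 10 − 0.10 × 6 = 9.4%, so it falls from 6.0 to 5.4 points.

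| Crossover c | Difference, sec. 8 | Power, sec. 8 | N per arm for 85% | Difference, sec. 7 | Power, sec. 7 | N per arm for 85% |
|---|---|---|---|---|---|---|
| 0 | 7.90 | 88.2% | 273 | 6.0 | 82.3% | 324 |
| 5% | 7.51 | 85.4% | 297 | 5.7 | 79.1% | 352 |
| 10% | 7.11 | 82.0% | 326 | 5.4 | 75.5% | 384 |
| 20% | 6.32 | 73.9% | 399 | 4.8 | 67.2% | 466 |
| 30% | 5.53 | 63.9% | 502 | 4.2 | 57.5% | 582 |

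Under section 8's rates, about 5% crossover uses up the margin above 85%. Under section 7's rates the pooled formula leaves no margin to begin with.

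**Sensitivity to the full-effect assumption.** Only the product of crossover share and relative effectiveness enters the formula. If outside CBT-I were half as effective as dCBTI, 20% crossover would give the 10% row: 82.0% or 75.5%.

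**The case against.** The strongest reply is that no crossover has been shown. The documents give no rate, and sections 3 and 4 describe CBT-I as under-used, with too few providers and barriers of time, cost and stigma. Those barriers would keep face-to-face crossover down, and nothing in the text supports 20 or 30% in particular. This stands, and it is why the figures above are conditional. It is only partly reassuring: recruitment runs in part through a sleep centre, and section 3 itself argues that digital delivery overcomes these barriers.

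The criterion can also be read more mildly, as accepting the behavioral approach that the trial offers. Section 5c describes outreach by phone and email, not a clinic waiting list. On that reading the new wording mostly clarifies. But the present wording also allows the literal reading, and no listed exclusion closes it off.

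The data-collection tool is in an appendix that is not in the text supplied. It may already record outside treatment, so a missing item cannot be claimed.

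A reader might infer three stronger things that the documents do not support:
- That the sample is full of people who have already had CBT-I. The database is one of several sources, and its members are described only as a "database (N=7608) of prior participants who have volunteered to be contacted for clinical trials". They are not said to have received CBT-I or joined CBT-I trials. Past CBT-I is also balanced between arms in expectation. It could reduce what dCBTI adds, but by an amount that cannot be found from the text.
- That the 2590 potential recruits in section 5c contradict section 5a because the count omits the treatment-choice condition. The count is a preliminary look at primary criteria ahead of a screening assessment. A choice made at recruitment cannot be counted in a database beforehand.
- That a null result would be uninterpretable. At 5 to 10% crossover under section 8's rates, power is still 85.4% to 82.0%.

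**Conclusion.** The point holds as a conditional risk that is cheap to remove. Section 5a, read literally, makes eligible a person who is in CBT-I or booked for it, and its listed exclusions do not prevent this. Outside CBT-I among controls would bias the as-randomised comparison toward no difference. For 5% to 20% crossover, the loss of power is about 3 to 14 points under section 8's rates (88.2% to 85.4% and 73.9%) and about 3 to 15 points under section 7's (82.3% to 79.1% and 67.2%).

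These losses rest on three assumptions: the crossover range itself, full dCBTI-level benefit in every control who crosses over, and no offsetting change in the dCBTI arm. The second puts the losses at the upper end for a given rate. It does not follow that crossover will occur at these rates, or that the contrast is already compromised.

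**What to change.** In section 5a, replace the condition of having chosen behavioral treatment with willingness to be assigned to either the online programme or the sleep-information e-mails. Add a screening exclusion for a current or scheduled course of CBT-I, in clinic or online.

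Do not exclude everyone who has ever completed CBT-I. That would narrow the population and shrink the pool by an unknown amount, to address a factor that randomisation balances in expectation. Record prior CBT-I at baseline instead.

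Confirm that the data-collection tool captures insomnia treatment received outside the trial at the post-treatment and 1-year assessments, and add an item if it does not. Keep the primary analysis as randomised, and report outside uptake by arm.

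The cost is a protocol amendment, one more screening question and a somewhat smaller pool. The loss from the pool cannot be sized from the documents, but the 600 required are 600/2590 = 23% of the preliminary database count, and section 5c names other sources.

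### The stated target is incident depression, but Section 7 models status at 1 year, and Sections 7 and 8 power the trial on different rates

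*Combined protocol and SAP*

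**What the plan says.** Section 2, Aim 1, is "to assess the efficacy of dCBTI for the prevention of incident depression among individuals with insomnia". Section 6b repeats the target: "The primary aim will be to reduce the incidence of depression". Section 8b gives the primary hypothesis in the same terms: "risk of depression incidence in the dCBT group relative to the control group will be analyzed using a multivariate logistic regression model".

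Section 7 is the only place that attaches a time point to the modelled outcome: "A logistic regression will be used to assess the association between treatment group and depression status at 1 year". Its power statement uses rates of 10% and 4% at 1 year (odds ratio 2.7), 300 per group, two-sided 0.05, and claims 85%. Section 8b uses other rates with the same sample size and alpha: "We anticipate a 14.6% rate of incident depression in the control group, compared to 6.7% in the treatment group", claiming more than 85%.

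Section 5a's only depression cut-off for entry is an exclusion of QIDS above 15 at recruitment. Section 6a gives the visit schedule, but its subject is insomnia and sleep symptoms: these "will be assessed at pre treatment, post treatment and at 1-year follow-up". Section 6b lists depression severity among the secondary, non-sleep measures, recorded by surveys that "will measure symptom improvements in severity of depression and work productivity", and gives no visit times for it. The data collection tool is in an appendix that is not part of the text supplied.

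**The concern.** Incidence over a year and status at one visit are different quantities. Status at month 12 depends on how many people became depressed and on how many of them recovered in time. A treatment that shortened episodes without preventing any would lower it, and Aim 1 is about onset.

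Misclassification can run both ways. An onset that resolves before the 1-year visit is recorded as no depression, so it counts as prevention. A participant who enters with symptoms at or below QIDS 15 and is unchanged at 1 year can be recorded as a case if the outcome threshold is lower than the entry limit, although nothing new has occurred. No passage restricts the Section 7 model to participants who are free of depression, by the outcome definition, at baseline.

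With two descriptions of the outcome and two pairs of rates, an analyst cannot tell from the text which endpoint is primary. That leaves the choice open until data are in hand.

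**Working it through.** **Inputs.** Section 7: 10% vs 4%, 300 per group, two-sided 0.05, stated power 85%. Section 8b: 14.6% vs 6.7%, same size and alpha, stated power above 85%.

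**Formula.** Pooled-variance two-proportion test: power = Φ[(p1 − p2 − 1.96·SE0)/SE1], with SE0 = √(2p̄(1 − p̄)/n), SE1 = √((p1(1 − p1) + p2(1 − p2))/n) and p̄ the mean of p1 and p2.

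**1. Section 8b.** p̄ = 0.1065, SE0 = 0.02519, SE1 = 0.02498. (0.079 − 0.04937)/0.02498 = 1.186, so power is 88.2%. The stated figure reproduces, for incidence.

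**2. Section 7.** p̄ = 0.07, SE0 = 0.02083, SE1 = 0.02069. (0.06 − 0.04083)/0.02069 = 0.927, so power is 82.3%. Exact enumeration gives 82.8% for the Wald test and 84.0% for Pearson; the arcsine approximation gives 83.9%. More conservative methods give less: Wald log-odds approximation 79.6%, Fisher 79.2%, continuity-corrected 77.8%. None reaches 85%; the pooled formula needs 324 per group for that. The odds ratio, (0.10/0.90)/(0.04/0.96) = 2.67, agrees with the stated 2.7. All figures are before any loss to follow-up.

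**3. Can one pair be derived from the other?** 10/14.6 = 0.68 in control and 4/6.7 = 0.60 in treatment. A single share of incident cases still depressed at 1 year would give equal ratios, and the documents state no link between the pairs. They cannot be treated as two views of one population.

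**4. Sensitivity, by assumption only.** Let f be the share of incident cases still depressed at 1 year, equal in both arms, applied to 14.6% vs 6.7% with 300 per group:

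| f | Rates | Power |
|---|---|---|
| 1.0 | 14.6% vs 6.7% | 88.2% |
| 0.9 | 13.1% vs 6.0% | 84.3% |
| 0.7 | 10.2% vs 4.7% | 73.3% |
| 0.5 | 7.3% vs 3.35% | 57.7% |

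The documents give no value of f. The table shows only why the Section 8b power cannot be carried over to a status outcome.

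**5. Would counting a case at either follow-up visit be better?** Assume uniform onset over 12 months, exponential episodes with d = median/ln 2, and post treatment at month 3. The share depressed at month 12 is (d/12)(1 − e^(−12/d)). The extra share caught at month 3 is (d/12)(1 − e^(−3/d))(1 − e^(−9/d)). Scenario A applies the same risk ratio throughout the year. Scenario B keeps the 12-month totals but has no effect before month 3, so treated onsets are 14.6%/4 = 3.65% by month 3 and 6.7% − 3.65% = 3.05% afterwards.

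| Median episode | Depressed at month 12 | Caught at either visit | Power A: 1-year status, either visit | Power B: 1-year status, either visit |
|---|---|---|---|---|
| 3 months | 34% | 50% | 42%, 57% | 63%, 43% |
| 6 months | 54% | 68% | 61%, 72% | 76%, 63% |
| 12 months | 72% | 81% | 75%, 80% | 82%, 76% |

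The either-visit outcome gains power under A and loses it under B. The documents do not decide between them.

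**The case against.** The strongest reply is that the plan never settled on point prevalence. Section 8b names incidence as the outcome of a logistic model too, so the Section 7 wording may be shorthand for any onset by 1 year, and the unseen appendix may hold an instrument with a look-back period. That stands in part: the defect is inconsistent and undefined wording, and a reader who infers a deliberate choice of prevalence goes further than the text. But no supplied passage says that status means onset by 1 year, and a look-back instrument would still need a rule turning its answers into the outcome.

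A reader might also infer that the trial collects depression data at post treatment and discards them. The Section 6a schedule covers insomnia and sleep symptoms, and QIDS appears only as an entry criterion. Post-treatment depression measurement is possible but not stated.

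It may be said that the recruitment pool has no depression, as Section 5c describes it. That is a description of database members, without an instrument or cut-off; the entry criterion itself is QIDS above 15.

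Finally, status at 1 year is a legitimate endpoint. It is, provided the aim and the conclusion are worded to match.

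**Conclusion.** The point holds as an inconsistency in endpoint definition. The aims and Section 8b target incidence, Section 7 as written analyses status at one visit, and each has its own rates. Two sizes are firm: 10% vs 4% with 300 per group gives about 82-84% power by the pooled and exact Wald or Pearson calculations, against a stated 85%; 14.6% vs 6.7% gives about 88%, which supports Section 8b only if incidence is analysed.

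The amount of misclassification and its effect on the treatment estimate cannot be derived. A reader might take the lower figures in the sensitivity tables as the trial's real power. They are not: they rest on assumed persistence, episode durations and onset timing. Nor do the documents support replacing the primary outcome with a case at either visit, since the effect on power changes sign with the assumed timing of the treatment effect.

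**What to change.** In Sections 7 and 8b, name one primary binary outcome for the logistic model: an incident case of depression by 1 year, with the instrument, threshold and any look-back period stated, among participants below that same threshold at baseline. If depression data are already collected before the 1-year visit, say how they count, at least in a supporting analysis. If only status at the 1-year visit is available, keep it and word the conclusion in those terms rather than as incidence.

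Use one pair of rates for that endpoint in both sections and restate the power. If 10% vs 4% is kept, replace 85% with about 82-84% and name the method. Keep 14.6% vs 6.7% only if incidence is what is analysed.

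The cost is protocol and analysis-plan wording, with the model and planned enrolment kept. The stated power becomes slightly less favourable if the Section 7 rates are kept, and participants at or above the threshold at baseline leave the primary analysis, so the power statement should use the number expected to remain.

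### The primary logistic regression has no method for a missing 1-year depression status, so it defaults to observed cases and is biased if the link between symptoms and dropout differs by arm

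*Combined protocol and SAP*

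**What the plan says.** Section 7 specifies the primary analysis in one sentence: "A logistic regression will be used to assess the association between treatment group and depression status at 1 year". It adds: "This approach allows inclusion of covariates in the model". The only covariates identified anywhere are histories of other sleep disorders (Section 5a). Section 8b repeats the logistic model for the primary hypothesis.

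The sample size statement is "We plan on enrolling a total of 300 subjects per group", and the power statements in Sections 7 and 8 both count all 300 per arm. The supplied text contains no expected dropout, inflation of the sample size, definition of the analysis set, imputation, weighting or sensitivity analysis. Section 6c says no limitations are expected.

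Three design features bear on who might be missing and what is known about them:

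- Section 5a: participants must "have opted for behavioral treatment for insomnia as therapy at recruitment".
- Section 5b, on the control arm: "Subjects will be emailed sleep tips and sleep-related information". The other arm works through an online programme (Section 6a).
- Section 6a: "Insomnia and other sleep-related symptoms will be assessed at pre treatment, post treatment and at 1-year follow-up". Depression severity is to be measured by survey (Section 6b), but no visit times are given for it.

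**The concern.** A logistic regression cannot use a record without an outcome. With no other rule stated, anyone lost before 1 year leaves the primary analysis, and whatever was recorded for them at the post-treatment visit is not used.

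The design gives a plausible reason for people to leave the two arms for different reasons. Everyone enrolled wanted behavioural treatment. Half receive emailed tips, half must keep up with an online course, and the outcome is read a year later. If depressed participants drop out relatively more in one arm than in the other, the arms are no longer comparable among those observed. Adjusting for baseline covariates does not remove a difference that arises from symptom change after baseline.

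Aim 1 rests on this single comparison, and few events are expected: 300 × 0.10 + 300 × 0.04 = 42 with the Section 7 rates, or 300 × 0.146 + 300 × 0.067 ≈ 64 with the Section 8 rates.

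**Working it through.** **Inputs from the documents.** 300 per arm; two-sided alpha 0.05; 10% vs 4% (Section 7); 14.6% vs 6.7% (Section 8). Every loss rate and correlation below is an assumption. Odds ratios are control against dCBTI, so values above 1 favour dCBTI.

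**Step 1: the plan's own figures.** With all 600 analysed, 10% vs 4% gives 82.3% power by the pooled two-proportion formula and 83.9% by the arcsine formula, against the stated 85%. For 14.6% vs 6.7% the pooled formula gives 88.2%, consistent with the stated figure of above 85%. If 20% had no 1-year status (240 per arm), the pooled figures would be 73.2% and 80.3%.

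**Step 2: when the odds ratio is biased.** With true rate p, loss Ld among depressed and Ln among non-depressed participants, the observed rate is

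p(1 − Ld) / [p(1 − Ld) + (1 − p)(1 − Ln)].

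Taking odds in each arm,

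complete-case OR = true OR × [(1 − Ld)/(1 − Ln) in control] ÷ [(1 − Ld)/(1 − Ln) in dCBTI].

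If the two bracketed ratios are equal, the OR is unchanged. Retention (depressed/non-depressed) of 60%/80% in control and 52.5%/70% in dCBTI gives 0.75 ÷ 0.75 = 1, so an OR of 2.38 stays 2.38 although loss depends on both arm and depression. Bias needs unequal ratios.

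**Step 3: size with no true effect, 14.6% depressed in both arms.** Take control losing 20% at random, and dCBTI losing 50% of depressed and 28% of non-depressed participants:

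- dCBTI observed rate = 0.146 × 0.50 / (0.146 × 0.50 + 0.854 × 0.72) = 0.0730 / 0.6879 = 10.6%; control stays at 14.6%.
- Numbers observed: 240 control and 300 × 0.6879 = 206 dCBTI.
- OR = (0.80/0.80) ÷ (0.50/0.72) = 1.44.
- Difference 0.0399, pooled SE 0.0317, unpooled SE 0.0313. Rejection = Φ[(0.0399 − 1.96 × 0.0317)/0.0313] = Φ(−0.71) ≈ 0.24; the opposite tail is negligible.

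The same losses with 10% depressed in both arms give 10.0% vs 7.2%, OR 1.44 and rejection 18%. Other assumed losses at 14.6%:

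| Control lost, depressed / non-depressed | dCBTI lost, depressed / non-depressed | Complete-case OR | False-positive rate |
|---|---|---|---|
| 50% / 28% | 50% / 28% | 1.00 | 5% |
| 30% / 20% | 40% / 28% | 1.05 | 5.3% |
| 20% / 20% | 35% / 28% | 1.11 | 6.6% |
| 25% / 20% | 40% / 28% | 1.12 | 7% |
| 20% / 20% | 50% / 28% | 1.44 | 24% |

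**Step 4: direction.** If control retains 60% of depressed and 80% of non-depressed participants while dCBTI retains 70% of both, a true OR of 2.67 becomes 2.67 × 0.75 ÷ 1 = 2.00. A real effect is then understated.

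**Step 5: what imputation recovers.**

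- *Loss driven by a recorded post-treatment score.* Large-sample check, 80% retained in control at random, 70% in dCBTI, true OR 2.67: the complete-case OR is 3.02, 3.34 or 3.78 for correlations of 0.3, 0.5 or 0.7 between that score and the 1-year symptom level. Using the score within arm returns about 2.67 each time. In a trial-sized simulation (no effect, 14.6%, control loss 20% at random, dCBTI loss 23% rising with the score, correlations 0.6), complete cases show 14.6% vs 11.8% with 14% rejection. Multiple imputation by arm from baseline and post-treatment scores brings the bias to near zero and rejection to 4%.
- *Loss driven by post-treatment depression, but only baseline depression and post-treatment insomnia available.* With insomnia correlations of 0.3 to 0.6, the dCBTI rate moves from 11.7–11.8% to 13.4–14.0% against a true 14.6%. Taking 11.75% as the start, (13.4 − 11.75)/(14.6 − 11.75) = 58% and (14.0 − 11.75)/(14.6 − 11.75) = 79% of the bias is removed. A second check gave about 55% to 75%.
- *Loss driven by the 1-year state itself.* The complete-case OR is about 4.7 against a true 2.67, and imputation brings it only to 4.50, 4.22 or 3.74 for correlations of 0.3, 0.5 or 0.7. That removes roughly 8% to 47% of the bias.

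**The case against.** The sponsor's statistician could fairly say five things.

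1. *The plan never says that only completers are analysed.* Correct. That is inferred from silence and from how a logistic regression behaves. Sections 6e and 8b also point to an appendix and a strategy section that are not in the supplied text. What stands is that no passage counters the default.

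2. *Symptom-related dropout does not by itself bias an odds ratio.* Correct, and Step 2 shows it. A reader might infer that any loss related to depression invalidates the comparison. The algebra does not support that; a difference between arms in the symptom–dropout link is required.

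3. *Differential dropout is speculation, and the 24% case is adverse.* The documents give no retention or engagement data, and milder inputs leave the error rate at 5–7%. The 24% figure is an illustration, not a forecast. Equally, nothing in the plan justifies assuming the link is the same in both arms.

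4. *The post-treatment data may not be the data needed.* Section 6a schedules only insomnia and sleep-related symptoms at that visit, and QIDS appears only as a recruitment exclusion. A reader might infer that a post-treatment depression score is already in hand; the documents do not say so. Sleep scores alone still helped in Step 5, under assumed correlations.

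5. *The simulations that favour imputation meet its own assumption.* True. Where loss follows unrecorded later symptoms, imputation removes less than half of the bias, so a sensitivity analysis is needed as well. Weighting could be used instead of imputation; that choice is partly preference.

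**Conclusion.** The point holds in conditional form. The plan names no method for a missing 1-year status, so its primary model defaults to observed cases and leaves the planned post-treatment assessment unused. The resulting odds ratio is biased, in either direction, if the symptom–dropout link differs between arms, and unbiased if it is multiplicatively the same in both.

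The size cannot be derived from the documents. Under the assumed losses in Step 3, the false-positive rate runs from about 5–7% to 24% at a 14.6% event rate. That range rests entirely on those assumptions. The supplied text does not support saying that the trial will be biased, that the plan prescribes a completers-only analysis, or that the recorded data would correct most of the problem whatever the cause of dropout. The change should be made because Aim 1 depends on this one comparison and a method chosen after dropout has been seen is open to challenge.

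**What to change.** In Section 7:

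- Define the primary analysis set as all randomised participants, in their assigned arm.
- Multiply impute 1-year depression separately by arm, using baseline QIDS, post-treatment insomnia and sleep scores, the model covariates, and a post-treatment depression score if one is collected. The sponsor should confirm whether it is, because Section 6 does not say.
- Fit the same logistic model to each imputed dataset and combine by Rubin's rules. Post-treatment scores belong in the imputation model only. Treatment affects them, so they should not be covariates in the primary model.
- Add a delta-adjusted (tipping-point) sensitivity analysis with delta varied separately by arm, since imputation corrects only the dropout that recorded data explain.
- Keep the complete-case fit as a sensitivity analysis.

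The cost is analysis-plan wording and a little more programming. The scheduled sleep and insomnia assessments need no new visits; whether post-treatment depression can be used depends on the sponsor's answer. The trade-off is that the primary result then relies on a missing-at-random assumption, which the tipping-point analysis probes.
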